Title: The diagnosis and treatment of *Chlamydia trachomatis* and *Neisseria gonorrhoeae* in pregnant women to prevent adverse neonatal consequences.”

CT/NG to neonates; and 3(c): To assess the frequency and distribution of Sample Adequacy Control (SAC) cycle threshold ( $C_t$ ) values from the Xpert® CT/NG assay, which may be a marker of inflammation, and evaluate correlations with the transmission of CT/NG to neonates.

**Recruitment/Eligibility:** Eligibility criteria for the comparison group are identical to those in Aims 1 and 2. Data will only be collected from participants in the STI testing group.

**Specimen Collection, Transport, Processing and Storage:** A self-collected swab for cytokine measurement will be collected at the baseline, third trimester, and first postnatal care visit and stored at -80°C. A peripheral blood sample (2-4mL) will be collected at the baseline, third trimester, and postnatal study visits. The blood sample will be processed and aliquots of EDTA plasma will be stored at -80°C. The swabs and plasma samples will be transported in dry ice to Stanford University for processing. Luminex will be used to measure the concentrations of 48 cytokines in the 48-plex assay (including IL-1 $\alpha$ , IL-1 $\beta$ , IL-6, IL-7, IL-8, IL-10, granulocyte macrophage colony- stimulating factor [GM-CSF], interferon- $\gamma$  inducible protein [IP]-10, monocyte chemoattractant protein [MCP]-1, MIP-1 $\alpha$ , MIP-1 $\beta$ , and tumor necrosis factor [TNF]- $\alpha$ ). These cytokines were selected based on previously identified associations with genital infection. Additionally the pathogen-specific and SAC Ct results will be automatically generated for each self-collected vaginal sample tested using the Xpert® CT/NG assay at delivery.

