## 5. Characteristics of the Subject Population:

### a. Number of subjects / Sample size:

Pregnant women attending their first ANC care visit at 27 weeks gestation or less. Participants must be 15 years of age and not treated with azithromycin, doxycycline, cefixime, or ceftriaxone in the past 30 days.

**Specific Aim 1 (STI testing group):** We will recruit 250 study participants for CT and NG testing.

**Specific Aim 2 (Standard of care comparison group):** We will recruit 250 antenatal patients from designated study ‘standard of care’ clinics who will be enrolled as a comparison group receiving the standard care with additional IPV and partner services and postnatal care testing (Total N=500). Among participants who test positive during postnatal care, we will offer infant testing (Estimated N=30 infants).

For Specific Aims 1 & 2, study staff will remain at study clinics during operating hours for the duration of the recruitment period. We will consecutively screen all pregnant women for eligibility and offer enrollment to all eligible women.

**Specific Aim 3 (Inflammatory markers):** We will include women in the STI testing group (Estimated N=250).

**Specific Aim 4:** We will enroll an additional 400 antenatal patients for the PoC syphilis sub-study (200 will receive the standard of care and 200 will be offered PoC syphilis testing in addition to the standard of care)

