**Specific Aim 3** At the baseline, third trimester and postnatal care study visit, self- collected swabs  and plasma samples (2-4mL) will be collected from participants in the STI testing group, and used to measure cytokine concentrations. Cytokines will be identified using the Luminex xMAP® 48-plex assay method located at Stanford University in order to test immunologic factors associated with vertical CT/NG transmission by describing concentrations of inflammatory cytokines in participants who tested positive for CT/NG. We will also conduct a secondary analysis of data collected during maternal CT/NG testing at the first postnatal visit (Aim 2) will be performed to determine the association between the Xpert® CT/NG assay’s pathogen-specific cycle threshold value ( $C_t$ ), which is a marker for the burden of infection, and vertical transmission of CT/NG to neonates; and assess the frequency and distribution of Sample Adequacy Control (SAC) cycle threshold ( $C_t$ ) values from the Xpert® CT/NG assay, which may be a marker of inflammation, and evaluate correlations with the transmission of CT/NG to neonates.

**Specific Aim 4:** Women in the syphilis sub-study will be similarly recruited and enrolled as in Aim 1 and 2. All participants will receive the standard of care in Botswana for syphilis testing with additional IPV screening and partner services offered to those in Aims 1 and 2. A simplified data collection instrument will be used to collect sociodemographic and behavioral factors, and obstetric/medical information with additional questions related to patient costs incurred due to syphilis care. Participants recruited into the PoC syphilis testing clinic will provide a blood sample for PoC syphilis testing and treatment.

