- During the antenatal visits (1st antenatal care and a visit in the 3rd trimester), participants in the STI testing group will be asked to provide self-administered vaginal swab samples for CT/NG testing by the GeneXpert and cytokine testing by Luminex. Participants will also be asked to provide additional samples that will be stored for testing of *Trichomonas vaginalis*, bacterial vaginosis, and/or *Mycoplasma genitalium*. These samples will be stored at the BHP lab for no longer than 24 months. Participants will also be asked to provide a plasma sample, collected by a trained phlebotomist, for cytokine testing by Luminex.
- During the first antenatal visit, a sub-sample of participants in the standard of care group will be asked to provide two self-administered vaginal swabs for testing after study completion. These samples will be immediately de-identified and stored at the BHP lab for no longer than 24 months.
- During the 1st antenatal care visit, participants in the syphilis PoC clinic will be asked to provide a blood sample for either dual HIV/syphilis or rapid syphilis point-of-care testing, which is offered in addition to the standard of care.
- During postnatal care, all participants will self-collect a vaginal sample for CT/NG testing by the GeneXpert. Participants in the testing group will self-collect an additional vaginal sample and will provide a plasma sample for cytokine analysis. Those who test positive will be offered infant testing via ocular/nasopharyngeal samples. Infant samples will be collected by a trained study nurse. Participants will also be asked to provide additional samples at the postnatal visit that will be stored for testing of *Trichomonas vaginalis*, bacterial vaginosis, and/or *Mycoplasma genitalium*. These samples will be stored at the BHP lab for no longer than 24 months.
- Postnatally, a sub-set of 35 participants who were treated for CT/NG, an STI syndrome or syphilis at any point during the study will be asked additional questions by study staff, expanding on partner

Title: The diagnosis and treatment of *Chlamydia trachomatis* and *Neisseria gonorrhoeae* in pregnant women to prevent adverse neonatal consequences."

notification and treatment experiences. These patients will additionally be asked if they are willing to refer their partner to participate in a semi-structured interview. If so, they will sign an informed consent allowing the study team to contact their partner(s).

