Prevalence of each STI will be measured as the proportion of individuals testing positive for a given STI divided by the number of individuals tested at each time point. Exact binomial 95% confidence intervals for prevalence will be estimated. Incident infections will be identified when a participant tests negative for an STI during her first ANC visit and positive for an STI during follow-up visits. Time at risk will be the length of time between the first test date and the positive test date. Correlates of CT/NG infections will be identified using both bivariate analyses and multivariate analyses.

Our primary outcome (mother-to-child transmission of CT and NG) and secondary outcomes (composite of preterm birth and/or low birth weight, and prevalence of maternal CT/NG infection at delivery) will be assessed using intention to treat analysis at the clinic level. We will conduct both unadjusted and adjusted analyses, including risk factors for maternal STI and neonatal infection that may be imbalanced between the testing and standard-of-care clinics. Effect measures will be estimated with 95% confidence intervals. All analyses will be carried out using the latest version of Stata statistical software (17.0 or higher; College Station, TX, USA).

To assess immune/inflammatory markers, multiple logistic regression models will be developed in an iterative process to identify individual cytokines and groups of cytokines associated with mother-to-child

transmission of CT/NG, preterm birth, and low birth weight. Additionally, we will identify plasma cytokine signatures that classify study participants with or without preterm birth/low birth weight infants.(1) We will define three equal frequency tertiles or “bins” (low, medium, and high), using all plasma samples. Next, we will use the VSURF R package, a random forest method to select the most predictive cytokines to differentiate samples from participants with and without preterm birth/low birth weight infants.(2) From these, we will build a decision tree to classify the samples. To better calibrate the accuracy of the decision tree, we will perform permutation testing.

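### The SAP does not restrict the preterm/low-birth-weight cytokine signature to plasma drawn before delivery, so as written up to one third of the samples post-date the outcome

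*SAP*

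**What the plan says.** **Sampling.** The protocol (section 3, Specific Aim 3, specimen collection) states: "A peripheral blood sample (2-4mL) will be collected at the baseline, third trimester, and postnatal study visits". Section 6 repeats the three visits and says that the specimens "will be collected from participants in the STI testing group, and used to measure cytokine concentrations". Section 7a confirms that the postnatal draw is meant for this purpose: "Participants in the testing group will self-collect an additional vaginal sample and will provide a plasma sample for cytokine analysis". Section 5a gives the number of women: "We will include women in the STI testing group (Estimated N=250".

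**Analysis.** The SAP (Statistical analysis, paragraph on immune and inflammatory markers) describes a plasma signature for preterm birth or low birth weight, built in four steps:

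1. Cytokine values are cut into tertiles: "low, medium, and high), using all plasma samples".
2. VSURF is used to "select the most predictive cytokines to differentiate samples from participants with and without preterm birth/low birth weight infants".
3. "From these, we will build a decision tree to classify the samples".
4. "To better calibrate the accuracy of the decision tree, we will perform permutation testing".

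**Outcome timing.** The SAP's secondary outcome list defines preterm birth by gestation at delivery (before 37 weeks) and low birth weight by weight at birth (under 2500 g). Both are settled by the time of delivery.

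Neither document limits the signature to antenatal draws, analyses it by visit, or says how several samples from one woman are handled.

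**The concern.** A postnatal plasma sample is taken after the outcome is known. Its cytokine levels can reflect the delivery, its complications or recovery. If such samples enter the selection step, a cytokine can be chosen because the birth changed it, when it carried no information beforehand.

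Permutation testing does not protect against this. It asks whether the classifier does better than it would with shuffled outcome labels. A postnatal difference between cases and non-cases is a real association in the data, so it passes the test. The test carries no information on which came first.

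At stake is how a listed secondary outcome can be read: the SAP names cytokines associated with preterm birth and low birth weight among its maternal outcomes. A signature partly driven by post-delivery samples could not be taken as describing the state of the pregnancy before the birth.

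**Working it through.** The plan gives no figure of its own for this analysis, so there is none to reproduce.

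**Step 1. Share of samples after the outcome.** Inputs: 250 women (protocol section 5a) and three plasma visits (protocol section 3), one of them postnatal.

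- Total if every visit is attended: 250 × 3 = 750. Postnatal: 250. Share: 250/750 = 33%.
- At the SAP's evaluable number per arm (232, Sample size section): 232 × 3 = 696. Postnatal: 232. Share: 232/696 = 33%.
- Left after restriction to antenatal draws: at most 500 of 750, or 464 of 696.

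These are upper limits, since not every visit will be attended.

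**Step 2. Can a post-delivery change alone get a marker selected?** This is an illustration by simulation. None of the following assumptions comes from the documents except the 250 women and three visits:

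- preterm/low-birth-weight frequency 10% or 20%;
- one cytokine, SD 1, within-woman correlation 0.5;
- no difference between cases and non-cases at baseline or in the third trimester;
- in cases, the postnatal value is shifted by 0, 0.5 or 0.8 SD;
- Mann-Whitney test at p<0.05 as a simple stand-in for VSURF;
- 2,000 simulated cohorts per scenario (simulation error about one percentage point).

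Percentage of runs in which the cytokine is flagged:

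| Cases | Postnatal shift | One mean per woman, all three visits | One mean per woman, antenatal visits only | All samples pooled as independent |
|---|---|---|---|---|
| 10% | 0 | about 5 | about 5 | about 17 |
| 10% | 0.5 SD | about 15 | about 5 | about 32 |
| 10% | 0.8 SD | about 32 | about 5 | about 54 |
| 20% | 0 | about 5 | about 5 | about 17 |
| 20% | 0.5 SD | about 25 | about 5 | about 45 |
| 20% | 0.8 SD | about 52 | about 5 | about 71 |

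**Step 3. Separate the two effects.** The third and fourth columns differ only in whether the postnatal sample is used. That gap (15–52% against about 5%) is the timing effect. The last column adds a second effect, because it treats three correlated samples from one woman as three independent units. Its size alone shows in the zero-shift rows: about 17% against a nominal 5%. The SAP's wording permits both effects, since it classifies samples and states no handling of repeats.

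**Step 4. Size in terms of discrimination.** In the pooled analysis the area under the ROC curve is 0.50 with no shift, about 0.55 with a 0.5 SD shift and about 0.57 with 0.8 SD. A single affected marker is therefore selected often but discriminates weakly.

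**The case against.** **The phrase about all plasma samples governs only the binning step.** This is literally true. It may also mean cut-points taken from cases and non-cases together, and not from every visit. A reader might infer that the SAP expressly puts postnatal samples into VSURF and the tree. It does not say that. But the later steps refer only to samples, define no narrower set, and follow directly from the binning sentence. Using the same set throughout is the natural reading, and nothing rules it out. If only the binning were affected, the harm would be small, because tertile cut-points do not use the outcome.

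**The SAP makes no forecasting or causal claim.** A reader might infer that the signature is offered as a predictor or a pathway. The SAP speaks of classification and association, and its reference to predictive cytokines describes variable selection. In the protocol, Aim 3 concerns vertical transmission, not preterm birth. This limits the consequence. It does not remove the defect, since even an association needs a stated time order to be interpretable.

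**The figures rest on assumed shifts and on one marker.** This stands. A single test is not VSURF across 48 cytokines. The pooled rates of 45% and 71% at 20% cases might be taken as the size of the timing problem, but they include the separate error of ignoring repeat samples.

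**Visit mix.** A reader might add that women who deliver early miss the third-trimester draw, so that sample mix depends on outcome. The mechanism is possible but close to negligible. With an assumed 30% against 5% missing, the area under the curve was no more than about 0.52. The documents give no such figures and no week for that visit.

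**Conclusion.** The point holds as a gap in the specification. The SAP sets no visit restriction on the plasma entering the preterm/low-birth-weight signature, and the protocol collects postnatal plasma for cytokine analysis. Followed as written, up to one third of samples post-date the outcome, markers altered by delivery can be selected, and the planned permutation test would not show it.

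The one-third share follows from the documents, on full attendance. The flag rates do not: they depend on the assumed frequency, shift and correlation, and show only that the effect need not be trivial. The timing defect itself does not depend on them.

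The importance is moderate. This is one exploratory classifier within a secondary outcome. The primary outcome, the sample size and the comparison of testing with standard care are unaffected. The documents also do not support a claim that the baseline sample must be the main analysis or that gestational age must be an input. Those are design preferences beyond what the defect requires.

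**What to change.** Amend the SAP paragraph on immune and inflammatory markers to state that:

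- the tertiles, the VSURF selection and the decision tree for preterm birth/low birth weight use only plasma taken before delivery;
- either each model uses one sample per woman, with baseline and third trimester analysed separately and the third-trimester model confined to women still pregnant at that visit, or, if visits are combined, all resampling and permutation is done by woman;
- postnatal plasma is reported descriptively and not as a classifier of birth outcome.

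If antenatal samples were intended all along, the first statement settles the matter.

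The cost is SAP wording, with no new data. The downside is fewer samples in the classifier: at most 500 of 750 across the two antenatal visits, or at most 250 in a single-visit model.

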The sample size of 500 participants was determined to have sufficient power to detect a difference in rates of vertical transmission of CT and NG based on 1) the prevalence of CT and/or NG among pregnant women in Botswana (10%),(5) and 2) the risk for vertical transmission of CT/NG to newborn infants during parturition (50%).(49-52). Antenatal CT/NG testing and treatment is expected to reduce vertical transmission by over 85%, from 5% in the control to 0.7% in the intervention group.(49, 50) When accounting for a 7% loss to follow-up rate, 250 women per arm will yield N=232 evaluable subjects. With N=232 evaluable samples per arm, we achieve 80.7% power to detect a 4.3% absolute difference in our primary endpoint, which is the proportion of vertical transmission of CT/NG, between the two groups, using a one-sided Fisher's Exact test, at a 0.05 significance level.

Methods for minimizing bias

Enrollment statistics, including total number of women attending their first antenatal clinic visit, total enrolled, total ineligible, and total who declined to participate, will be recorded in a weekly tally sheet and presented at bimonthly study meetings. Participant characteristics, such as sociodemographic characteristics, gestational age, HIV infection status, syphilis test results, obstetric history (e.g. history of preterm birth), in the testing and standard-of-care clinics will be monitored and compared to assess balance. Attrition will also be monitored and attrition bias will be assessed on a monthly basis.

Data Management

Data will be collected and managed using REDCap electronic data capture tools hosted at the Botswana Harvard AIDS Institute Partnership (BHP). REDCap (Research Electronic Data Capture) is a secure, web-based software platform designed to support data capture for research studies, providing 1) an intuitive interface for validated data capture; 2) audit trails for tracking data manipulation and export procedures; 3) automated export procedures for seamless data downloads to common statistical packages; and 4) procedures for data integration and interoperability with external sources.

Data will be entered offline at study clinics into CRFs on the REDCap mobile application on study tablets. At the end of each working day, data will be checked for any errors, discrepancies and missing data

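### The plasma cytokine tree is scored on the samples that chose its markers, so its accuracy will read too high; the planned permutation test, whose scope is not stated, does not correct that

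*SAP*

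**What the plan says.** The SAP, under Statistical analysis, sets out four steps for the plasma signature.

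1. Coding: "We will define three equal frequency tertiles", with the cut points taken "using all plasma samples".
2. Selection: VSURF, described as "a random forest method to select the most predictive cytokines to differentiate samples" by preterm birth/low birth weight status.
3. Classifier: a decision tree built from the selected cytokines to classify the samples.
4. Assessment: "To better calibrate the accuracy of the decision tree, we will perform permutation testing".

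Nothing more is said about validation. The SAP does not give the accuracy metric, the significance level, the number of markers kept, the tree size, the expected number of cases, or which of these steps is repeated under permutation.

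The protocol gives the scale. Section 3, Specific Aim 3: "Luminex will be used to measure the concentrations of 48 cytokines in the 48-plex assay", and "A peripheral blood sample (2-4mL) will be collected at the baseline, third trimester, and postnatal study visits". Section 5a limits Aim 3 to the STI testing group, an estimated 250 women. The SAP's Sample size section adds: "When accounting for a 7% loss to follow-up rate, 250 women per arm will yield N=232 evaluable subjects".

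**The concern.** Two separate problems follow from this sequence.

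First, the tree is judged on the samples that chose its markers and its splits. With 48 candidates, some will separate cases from non-cases by chance, and the tree exploits exactly those. VSURF uses out-of-bag error internally, but that does not cover the tree, which is a different model fitted afterwards to markers already chosen with the outcome.

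Second, permutation is given the task of calibrating accuracy. It shows how large the score could be by chance. It does not show how well the tree would classify new women. Even the chance reference is valid only if the permuted runs repeat everything that used the outcome. If the markers stay fixed at those chosen with the true labels, the permuted trees have lost the advantage that the real tree keeps.

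At stake is a listed secondary outcome: a signature could be reported with inflated accuracy, or reported when there is none.

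**Working it through.** The plan states no accuracy or error rate for the classifier, so there is no figure of its own to reproduce. The check is a simulation in which no cytokine carries any information.

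**Inputs from the documents.** 48 markers (protocol section 3); tertile coding (SAP); 250 × 0.93 = 232.5, taken as 232 women (SAP, Sample size).

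**Assumptions, because the documents are silent.** 20% cases (232 × 0.20 ≈ 46), with 12% also tried; one sample per woman; 1 to 8 markers kept; tree depth 3 with leaves of at least 5 to 7; one-sided 5% level; score either AUC or plain accuracy (proportion correctly classified). The VSURF package was not available. Markers were ranked by random-forest importance or chi-square, or chosen by a hand-coded VSURF-like selector (importance threshold, then nested out-of-bag models, without VSURF's final prediction step).

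**Test.** With B permutations, p = (1 + number of permuted scores ≥ observed score)/(B + 1); a signature is declared if p ≤ 0.05. In the table, only the tree is refitted under permutation, with the selected markers held fixed. The first seven rows use 60 data sets and B = 79; the last uses 80 data sets and B = 99.

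| Women | Cases | Selection | Mean apparent AUC | False positives, AUC | False positives, accuracy |
|---|---|---|---|---|---|
| 232 | 20% | forest, 3 kept | 0.72 | 70% | 30% |
| 232 | 20% | forest, 5 kept | 0.74 | 65% | 35% |
| 232 | 20% | forest, 8 kept | 0.76 | 52% | 35% |
| 232 | 20% | chi-square, 5 kept | 0.74 | 62% | 27% |
| 232 | 20% | forest, 5 kept, markers correlated 0.4 | 0.72 | 52% | 27% |
| 232 | 12% | forest, 5 kept | 0.79 | 60% | 37% |
| 100 | 20% | forest, 5 kept | 0.83 | 58% | 40% |
| 232 | 20% | VSURF-like, 1 to 8 kept | 0.62 | 50% | 11% |

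Monte Carlo error is √(p(1−p)/R); for 65% of 60 data sets that is √(0.65 × 0.35/60) ≈ 6 points.

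**Accuracy.** The true AUC is 0.50 by construction. As a direct check, trees from the chi-square, five-marker setting were applied to new simulated women; their mean AUC was 0.50. The optimism at five markers is therefore about 0.74 − 0.50 = 0.24. With the VSURF-like selector it is about 0.62 − 0.50 = 0.12.

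**Permutation with selection repeated.** Reranking the markers in every permutation (chi-square, five kept, B = 59) gave 5/60 = 8% false positives, with standard error √(0.083 × 0.917/60) ≈ 3.6 points. A separate run with 230 women and 120 data sets gave 6%. Both are consistent with 5%.

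**Why the lowest figure is 11%.** The VSURF-like selector kept one marker in 66 of 80 data sets. A tertile holds about 232/3 ≈ 77 women, so a leaf that predicts 'case' would need at least 39 of the 46 cases, when about 46/3 ≈ 15 are expected. A one-marker tree therefore predicts 'non-case' for everyone and scores 186/232 = 80.2% under real and permuted labels alike, so it cannot reject. The 9 rejections (0.1125 × 80) must come from the 14 data sets with four or more markers. The 11% thus reflects a metric that often cannot move. It is not evidence that the test is sound.

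**The case against.** **Scope of the permutation.** A reader might infer that the SAP permutes only the finished tree. The sentence follows the selection step and names only the tree, but it does not say which steps are repeated. Rerunning VSURF as well fits the wording, and the false-positive rate is then close to 5%. The study cited for the approach might settle this, but it is not available here. This part of the objection stands: the scope is unspecified, and no error is written into the plan.

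**Size.** A reader might also infer that a false signature would appear in about two of three noise data sets. That holds only for an AUC score with roughly three to five markers forced in. The SAP's own word is accuracy and its selector is VSURF; the nearest setting tried gave 11%. The simulations also use one sample per woman, whereas the plan collects up to three. This stands too: only a conditional range can be given.

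**Meaning of calibrate.** Reading the apparent accuracy against its permutation distribution is a sensible use of the method, and the SAP promises no formal significance claim for the tree. But the accuracy reported would still be the apparent one, even with the whole pipeline permuted. On this the objection fails.

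**Tertiles.** One might fault the binning as well. The cut points do not use the outcome, so they create neither optimism nor false positives, and the simulations do not test them. Binning is not part of this point.

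**Conclusion.** The plan as written yields only apparent accuracy for the plasma signature, and that will be biased upward. This needs no simulation, since nothing is held out and no correction is described. Its size rests on assumptions: with no signal, 232 women, 20% cases and five markers kept, the AUC reads about 0.74 instead of 0.50. Across the settings tried it reads 0.62 to 0.83.

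The permutation step does not remove this bias, and its scope is open. If only the tree is permuted, the false-positive rate is above 5% in every setting tried, roughly 11% to 70%. If selection is repeated, it is near nominal. The documents do not support saying that the SAP has chosen the faulty version.

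The classifier belongs to a secondary outcome, and the primary comparison does not depend on it. The change should still be made, because a better procedure is available at little cost.

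**What to change.** Amend the SAP's paragraph on immune/inflammatory markers as follows.

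- Run VSURF and tree fitting together inside repeated cross-validation, and report the cross-validated AUC, sensitivity and specificity as the accuracy of the signature.
- Split by woman. Plasma is taken at up to three visits, and one woman's samples must not fall on both sides of a split. State which visit or visits are analysed.
- For any permutation test, name the score, permute outcome labels by woman before VSURF, and rerun the whole pipeline in each permutation.

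No further data or samples are needed. The cost is SAP wording, computing time (VSURF is rerun in every fold and every permutation) and a lower reported accuracy.
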